16.0 Financial Considerations

16.1 * PAYMENT: Will subjects be paid for participation, reimbursed for time or expenses, or receive any other kind of compensation: (REQUIRED)

Yes No

16.2 PAYMENT METHODS: Subjects payment or compensation method (check all that apply):

Payments will be (check all that apply):

- Cash
- Check
- Gift card
- Debit card
- UCSF Research Subject Payment Card
- Reimbursement for parking and other expenses
- Other:

Specify **other** payment/compensation method:

Paypal electronic cash transfers.

16.3 PAYMENT SCHEDULE: Describe the schedule and amounts of payments, including the total subjects can receive for completing the study:

- If there are multiple visits over time, explain how payments will be prorated for partial completion
- If deviating from recommendations in Subject Payment Guidelines, include specific justification below

Participants will be compensated for their time at each visit and in responding to daily ecological momentary messages (up to a total of \$556). Participants will receive \$80 for the 2 screening visits (\$35 at Screen 1 and \$45 at Screen 2), \$15 for run-in visits 1 and run-in visit 2, \$55 for enrollment, \$20 for weekly visits (1-3, 5-7, and 9- 11), \$55 for week 4 (month 1) and week 8 (month 2) visits, and \$65 for week 12 (month 3). In addition, they will receive \$0.40 for each day that they complete the daily EMA series throughout the 12-week treatment period (up to \$36).

Participants could receive a gift card (\$10) for partial screening visits. Participants could receive a gift card (\$20) if they confirm and arrive at their scheduled screen 1 in-office visit. Participants who are given loaner phones could receive \$50 if they return the loaner phone at the week 12 visit.

For any snowball referral that has completed a screening visit, the participant who referred the new participant will receive \$10. If the new participant enrolls in the study, the participant who referred the new participant will receive \$40.

16.4 COSTS TO SUBJECTS: Will subjects or their insurance be charged for any study activities:

Yes No

17.0 Other Approvals and Registrations

17.1 * ADMINISTRATION OF RECOMBINANT DNA: Does this study involve administration of vaccines produced using recombinant DNA technologies to human subjects (Help Link added Aug '15): (REQUIRED)

Yes No

17.2 * HUMAN GENE THERAPY: Does this study involve human gene therapy: (REQUIRED)

Yes No

17.4 OTHER APPROVALS: Indicate if this study involves other regulated materials and requires approval and/or authorization from the following regulatory committees:

Institutional Biological Safety Committee (IBC)

Specify BUA #:

Institutional Animal Care and Use Committee (IACUC)

Specify IACUC #:

Controlled Substances

19.0 End of Study Application

End of Study Application Form

To continue working on the Study Application:

Click on the section you need to edit in the left-hand menu. Remember to save through the entire Study Application after making changes.

If you are done working on the Study Application:

Important: Before proceeding, please go back to Section 4.0 Initial Screening Questions and **Save and Continue** through the form to make sure all the relevant sections and questions have been included. If you've changed any answers since you started, the branching may have changed. Your application will be incomplete and it will have to be returned for corrections.

Once you are sure the form is complete, click **Save and Continue**. If this is a new study, you will automatically enter the **Initial Review Submission Packet Form**,

where you can attach **consent forms** or other **study documents**. Review the [Initial Review Submission Checklist](#) for a list of required attachments.

Answer all questions and attach all required documents to speed up your approval.

The UCSF IRB welcomes feedback about the IRB Study Application Form. Please click the link to answer a [survey](#) about the application form.

**07/13/2021**

## Statistical Analyses

We will use generalized estimating equations (GEE) to estimate treatment effects on repeated study outcomes. Primary analyses will be by intention-to-treat (ITT). In prior trials, we had excellent visit retention and study completion. Nonetheless, in this high-risk population, missing data may be encountered. We will conduct sensitivity analyses imputing all missing urine samples as positive, adjusting for baseline correlates of missingness, and using inverse probability of censoring weights.

**Specific Aim 1:** *To determine the efficacy of ION vs. placebo in reducing meth use, as determined by the proportion of meth-positive urine tests.* As in our prior trial, a GEE Poisson model with robust standard errors will be used to compare weekly urine test results by treatment assignment; this provides easier-to-interpret risk ratios rather than odds ratios. The treatment effect of ION vs. placebo will be modeled as linearly increasing and summarized by the between-group difference in means at 12 weeks, net of any baseline difference.

**Minimum Detectable Effects (MDEs) with sample size:** Based on the prior trial (93% retention), we estimate that 90% of participants will be retained at 12 weeks, and within-subject correlation will be 0.45. Under these assumptions, the study sample of 54 participants will have 80% power in 2-sided tests with a type-I error rate of 5% to detect net between-group differences in the reduction in urine positivity of ~24 percentage points, equivalent to a relative rate reduction of 32%. We have observed similar reductions on meth use in ITT and subgroup analyses in prior trials. Therefore, we believe that the reductions in meth use we are powered to detect in this aim are reasonable to anticipate.

**Specific Aim 2:** *To determine the efficacy of ION vs. placebo in reducing meth-associated sexual risk behaviors.* We will use GEE Poisson models with robust standard errors to assess evidence that the intervention reduces HIV risk behaviors, including number of sex partners, and number of sex partners with whom meth is used.

**MDEs:** Using data from our prior trial on baseline means, within-subject correlation, and over-dispersion, we estimate that the study sample of 54 participants will have 80% power to detect ~46% net reductions in the numbers of sexual partners and ~67% reductions in partners with whom meth is used. In our Project iN study, we have observed statistically significant reductions on sexual risk outcomes ranging between 85%-89% among the treatment arm, compared to placebo. Therefore, given the results from the prior trial, we believe that the reductions we are powered to detect in this aim are reasonable to anticipate.

**Specific Aim 3:** *To determine the efficacy of ION vs. placebo in increasing PrEP adherence among HIV-negative participants and ART adherence among participants living with HIV, as measured by serum drug levels and viral suppression rates.* We will use GEE Poisson models with robust standard errors to assess evidence that the intervention increases PrEP and ART adherence.

**MDEs:** Using the assumptions for loss to follow-up from Project iN for Aim 1, and informed by the within subject correlations of a PrEP adherence measure in the EPIC study and of detectable viral loads among HIV+ participants in a Mirtazapine trial for MSM who use meth, we estimate that the study sample of 54 participants will have 80% power to detect 10-19 percentage point increases in PrEP/ART adherence, depending on within-subject correlations and adherence levels in the reference group.

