Study Site: Study activities will take place at the Center on Substance Use and Health (CSUH) of the San Francisco Department of Public Health (SFDPH), a well-established clinical trial site located at [name]. [name] has a joint appointment as a Senior Research Scientist at SFDPH. He has conducted research at this field site since 2008. The site is centrally located near multiple transit lines with convenient access for residents of multiple neighborhoods with high rates of alcohol use. As noted above, we have had remarkable success recruiting and retaining meth users at this location. Study staff have access to both SFDPH resources (see LOS from SFDPH Director [name]) and UCSF resources as described in the Facilities section. The paired effort of these institutions has proven highly effective in both research and clinical care in San Francisco.

Randomization: Randomization (2:1 for ION versus placebo) will occur using double-blind, block randomization. *Assignment of two-thirds of participants to the ION arm was chosen to improve our ability to 1) examine whether EMI leads to greater ION adherence, and reductions in meth use, and 2) enhance our ability to detect adverse events in the active treatment arm.* This ratio was also selected with the knowledge that it has a negligible impact on the study's minimum detectable treatment effects, compared to a 1:1 allocation (i.e., the difference in the detectable treatment effects between the 1:1 and 2:1 allocation ratios were minor across all primary outcomes), while retaining a stable size for placebo, in the event that some participants are lost to follow-up. The study biostatistician will generate a random allocation sequence list with treatment assignments associated with order of enrollment, using randomly permuted blocks with randomly selected block sizes 3 and 6. To ensure balance by HIV-status, allocation will also be stratified by HIV serostatus. To mask the randomized allocation sequence, the statistician will provide this stratified list to the study pharmacist.

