Specific Aim 1: *To determine the efficacy of ION vs. placebo in reducing meth use, as determined by the proportion of meth-positive urine tests.* As in our prior trial, a GEE Poisson model with robust standard errors will be used to compare weekly urine test results by treatment assignment; this provides easier-to-interpret risk-ratios²¹⁸ rather than odds-ratios. The treatment effect of ION vs. placebo will be modeled as linearly increasing and summarized by the between-group difference in means at 12 weeks, net of any baseline difference. *Minimum Detectable Effects (MDEs) with sample size:* Based on the prior trial (93% retention with an 8-week follow-up), we estimate that 80% of participants will be retained at 12 weeks, and within-subject correlation will be 0.45. Under these assumptions, the study sample will have 80% power in 2-sided tests with a type-I error rate of 5% to detect net between-group differences in the reduction in sweat patch positivity of ~14.5 percentage points. In the Project iN study, we have observed reductions on meth use between 18%-22% among the ION arm, compared to placebo, in ITT and sub-group analyses.¹⁰⁹ Therefore, we believe that the reductions in meth use we are powered to detect in this aim are reasonable to anticipate. *In sensitivity analyses*, we will also evaluate between-group differences on changes in: 1) any meth-positive samples or self-report of meth use in timeline follow back; and 2) meth positivity from self-report only. Concordance of the urine testing, and self-reported measures will be examined using weighted Kappa and correlations. We recognize that meth use is a stigmatized behavior that may be underreported. Hence, in the event of discrepancies between urine results and timeline follow back data on meth use, we will treat the urine test results as the gold standard. *Additionally, we will analyze participant's perception of whether the EMI prompts had effects on various HBM constructs and explore whether these moderate treatment effects on meth use.*^{119,120}

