Specific Aim 2: *To determine the efficacy of ION vs. placebo in reducing meth-associated sexual risk behaviors.* We will use GEE Poisson models with robust standard errors to assess evidence that the intervention reduces HIV risk behaviors, including number of sex partners, number of sex partners with whom meth is used and episodes of condomless sex with serodiscordant partners. *MDEs:* Using data from our prior trial on baseline means, within-subject correlation, and over-dispersion, we estimate that the study sample of 60 participants will have 80% power to detect ~46% net reductions in the numbers of sexual partners, ~67% reductions in partners with whom meth is used, and ~52% reductions in episodes of condomless sex with serodiscordant partners at 12 weeks. In our Project iN study, we have observed statistically significant reductions on sexual risk outcomes ranging between 85%-89% among the treatment arm, compared to placebo.¹⁰⁹ Therefore, given the results from the prior trial, we believe that the reductions we are powered to detect in this aim are reasonable to anticipate. *In sensitivity analyses*, we will examine how PrEP use and viral suppression status of participants and their partners (partner data assessed via self-reported egocentric data collection from participants)²¹⁹ modify treatment effects on sexual risk behaviors. We will also examine whether there is evidence of effect modification depending on whether both the study participant and partner, the

participant only, the partner only, or neither the participant nor the partner used a biomedical HIV prevention tool (PrEP or ART).²¹⁹

Specific Aim 3: *To determine the efficacy of ION vs. placebo in increasing PrEP adherence among HIV-negative participants and ART adherence among participants living with HIV, as measured by serum drug-levels and viral suppression rates.* We will use GEE Poisson models with robust standard errors to assess evidence that the intervention increases PrEP and ART adherence. *MDEs:* Using the assumptions for loss to follow-up from Project iN for Aim 1, we estimate that the study sample of 60 participants will have 80% power to detect 10-19 percentage point increases in PrEP/ART adherence, depending on within-subject correlations and adherence levels in the reference group.^{126,220}

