11.0 Sample Size and Eligibility Criteria

11.1 ENROLLMENT TARGET: How many people will you enroll:

60

If there are multiple participant groups, indicate how many people will be in each group:

The ION+EMI study will enroll 60 participants in the double-blinded placebo controlled clinical trial where 40 participants will receive Intermittent Oral Naltrexone and 20 participants will receive placebo.

11.3 SAMPLE SIZE JUSTIFICATION: Explain how and why the number of people was chosen. For multi-site studies, this is referring to the number that will be enrolled across all sites:

For the phase 2b clinical trial, a sample size of 60 was selected to provide 80% power in 2-sided tests with a type-I error rate of 5% to detect between a 18-22% reduction of meth use among the ION arm, compared to placebo, in ITT and sub-group analyses. We hypothesized on pharmacologic grounds that oral naltrexone will reach full efficacy against meth use almost immediately; accordingly we expect treatment-control differences to be approximately constant over the 12 weeks of the trial. Based on the prior trial (93% retention), we estimate that 90% of participants will be retained at 12 weeks. Under these assumptions, the minimum detectable effects for our outcomes are calculated as follows:

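### Aim 1 subtracts the enrollment arm difference instead of adjusting for enrollment urine, at a small cost in precision, and the Aim 1 and Aim 2 models omit the HIV-serostatus randomization stratum

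*SAP*

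**What the plan says.** **Aim 1 model.** In the SAP (Statistical Analyses, Specific Aim 1), "a GEE Poisson model with robust standard errors will be used to compare weekly urine test results by treatment assignment". The effect is then "summarized by the between-group difference in means at 12 weeks, net of any baseline difference". Protocol 8.13 and the Specific Aim 1 text in 11.3 describe the same model and summary. No section enters enrollment urine as a covariate, although Table 4 schedules urine at enrollment and weekly. No working correlation is named.

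**Effect shape.** Protocol 8.13: "The treatment effect of ION vs. placebo will be modeled as linearly increasing". The opening of protocol 11.3 instead supposes that "oral naltrexone will reach full efficacy against meth use almost immediately" and concludes that "we expect treatment-control differences to be approximately constant over the 12 weeks of the trial". A few lines later, 11.3 repeats the linear model.

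**Stratum.** Protocol 8.9 (Randomization): "allocation will also be stratified by HIV serostatus". The Aim 1 models do not mention serostatus. For Aim 2, "We will use GEE Poisson models with robust standard errors to assess evidence that the intervention reduces HIV risk behaviors", again with no baseline value or stratum named.

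**Other uses of baseline data.** Adjustment for baseline variables appears only as a missing-data sensitivity analysis (protocol 8.13 and SAP). The protocol's Aim 2 sensitivity analyses treat PrEP use and viral suppression as effect modifiers, which is not adjustment for the stratum.

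**Aim 3** is outside this point, because its outcomes are defined within serostatus: "increasing PrEP adherence among HIV-negative participants and ART adherence among participants living with HIV".

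**The concern.** Randomization makes the expected enrollment difference between arms zero. Subtracting the observed difference therefore removes chance imbalance but adds the sampling noise of the enrollment measurement. Conditioning on enrollment urine, or holding the arms equal at enrollment, uses the same data and usually gives a smaller standard error. With 18 to 20 placebo participants there is little precision to spare.

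A stratum used to randomize is ordinarily carried into the analysis model. Here it is left out by silence.

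Baseline handling also cannot be settled apart from the effect shape. A straight line that starts at enrollment and a step that is complete by week 1 need different baseline terms, and the documents describe both.

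**Working it through.** **Inputs.** From the SAP: 54 participants, correlation 0.45, 80% power, two-sided 5%, detectable difference about 24 points or 32% relative. From protocol 8.9: 2:1 allocation, so 36 vs 18. Implied rates: 0.24/0.32 = 0.75 on placebo and 0.75 - 0.24 = 0.51 on ION. Assumed: exchangeable correlation, observations at weeks 0 to 12, identity scale. Protocol 8.13 gives a different Aim 1 figure (about 14.5 points, for sweat patches, at 80% retention), which is not used here.

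**1. Reproduce the plan's figure.** The detectable difference d solves

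d = 2.802 × √{ f × [0.75×0.25/18 + (0.75-d)(0.25+d)/36] },

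where 2.802 = 1.960 + 0.842 and f is the variance factor of the week-12 contrast.

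Netted line (arm, week, arm-by-week): Σ(t-6)² = 182 over weeks 0-12, so f = 12² × 0.55/182 = 0.435. At d = 0.244 the bracket is 0.01042 + 0.00694 = 0.01736, and 2.802 × √(0.435 × 0.01736) ≈ 0.244. **The netted line gives 24.4 points, matching the SAP's figure of about 24.** Power at 24 points is 78.9%. With 60 participants the same model gives 23.1 points and 82.9%.

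**2. Same line, arms held equal at enrollment.** Σt² = 650, Σt = 78, and 0.45/(0.55 + 13×0.45) = 0.0703. Then f = 144 × 0.55/(650 - 0.0703×78²) = 79.2/222.2 = 0.356. **The detectable difference falls to 22.0 points**; power at 24 points is 86.2%.

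**3. Poisson GEE with robust standard errors, linear effect.** Simulated standard errors are 4-8% smaller with a common baseline. In the second generator, each result uses a person-level uniform draw with probability √0.45 and otherwise an independent one (3000 runs, no missing data).

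| Case | Power, netted | Power, common baseline |
|---|---|---|
| First generator | 83.1% | 83.4% |
| Second generator | 72.2% | 77.5% |
| Enrollment 90% positive, correlation with follow-up 0.39 | 75.0% | 74.6% |
| Enrollment 90% positive, correlation 0.20 | 70.8% | 71.1% |
| Enrollment 95% positive, correlation 0.20 | 73.6% | 71.2% |

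The last three rows (2000 runs each) are assumptions. They are plausible because protocol 11.7 requires at least weekly use and a positive screening sample. Null rejection in the second generator is 4.9% netted and 5.5% common baseline.

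**4. If the true effect is constant from week 1 (identity scale).**
- Netted line: Σ(t-6) over weeks 1-12 is 78 - 72 = 6, so the week-12 estimate recovers 12×6/182 = **0.40** of the effect.
- Line anchored at enrollment, exchangeable: 12 × (78 - 0.0703×936)/222.2 = 0.66, where 936 = 78×12.
- Same line, independence working correlation: 12×78/650 = 1.44.
- Single arm term on weeks 1-12 adjusted for enrollment urine: f = 0.45 + 0.55/12 - 0.45² = 0.293, a detectable difference of 20.0 points.

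**5. Shape or netting?** Three models were simulated under a constant effect (2000 runs): the netted line; netting kept but with a post-enrollment step and slope freed; and enrollment-adjusted arm plus arm-by-week terms on weeks 1-12. Power is 25%, 62% and 77%; shares recovered (log scale) are 0.48, 1.02 and 1.01. Of the 77 - 25 = 52 points, 62 - 25 = 37 come from the shape and 77 - 62 = 15 from baseline handling.

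**6. HIV serostatus.** Added to the arm plus arm-by-week model under a linear effect, with an assumed 40% prevalence, the term moves power from 74.5% to 74.5% (no difference in positivity between strata) and from 75.4% to 76.0% (15-point difference).

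**The case against.** The strongest reply is that the planned contrast is prespecified and valid, and that under the linear effect it assumes, little is lost. That stands. The 24.4 vs 22.0 comparison is an identity-scale approximation. The Poisson GEE gain is 0 to 5 power points, and near an enrollment ceiling the common-baseline model can be slightly worse (71.2% vs 73.6%). At 95% positivity only about three of 54 participants would be negative at enrollment, so the covariate would carry almost no information.

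It may also be said that netting could mean covariate adjustment. The wording does not exclude this, but the subtraction model is the one that reproduces about 24 points.

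A reader might infer three stronger things, none of which the documents support:
- **That netting biases the comparison.** It does not. Randomization gives both approaches the same target when the shape is right.
- **That netting alone loses most of the power**, from the 0.40 share in step 4 or the 25% vs 77% in step 5. Most of that loss comes from fitting a line through enrollment to a step. With netting kept and the shape freed, the share returns to about 1.0.
- **That omitting HIV serostatus inflates type I error or costs real power.** Neither is shown. Ignoring a prognostic stratum tends to make the test slightly conservative: actual alpha is about 0.048, 0.044 and 0.039 if the stratum is assumed to explain 2%, 5% and 10% of outcome variance.

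On Aim 2, the SAP states its detectable effect on sexual partners as a net reduction and draws on baseline means from the prior trial. Baseline may therefore already enter by subtraction; the text does not say.

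**Conclusion.** The point holds as a modest, low-cost improvement. Aim 1 uses enrollment urine only by subtraction, and the Aim 1 and Aim 2 models omit the randomization stratum. Under the planned linear effect, the cost of netting is 2.4 points of detectable difference (24.4 vs 22.0) on the approximation and 0 to 5 points of simulated power, falling to about nil if 90-95% of enrollment samples are positive. This rests on 18 vs 36 participants, exchangeable correlation 0.45 and 75% reference positivity. The documents do not give the enrollment positivity that decides where in the range the trial falls.

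The conflict between a constant and a linear effect is a separate and larger matter. It has to be settled first, because the right baseline term depends on it. No precision gain is claimed for the HIV term. No Aim 2 gain is quantified, because the baseline correlations are not in the documents.

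**What to change.** 1. Reconcile the constant effect in protocol 11.3 with the linear effect in 8.13, 11.3 (Specific Aim 1) and the SAP, and state one shape.
2. In Aim 1, replace the netting clause with baseline adjustment matched to that shape. **If linear:** keep enrollment as week 0, hold the arms equal there, use an arm-by-week term with no arm main effect, and name an exchangeable working correlation. **If constant:** use a single arm term on weeks 1-12, adjusted for enrollment urine.
3. Include HIV serostatus in the Aim 1 and Aim 2 models, justified by consistency with the stratified randomization.
4. In Aim 2, adjust each outcome for its enrollment value where one is collected. Table 4, as it can be read, covers numbers of partners and condomless acts but shows no enrollment measure of partners with whom meth is used. Confirm whether one exists.

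**Cost.** One SAP paragraph for Aim 1 and about a sentence for Aim 2, with no new data. The downsides are up to two covariate degrees of freedom with 18-20 placebo participants, little or no gain if nearly all enrollment urines are positive, and the sensitivity of the anchored line to effect shape and working correlation (0.66 vs 1.44 of a constant effect).
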